1. INTRODUCTION

1.1 Study overview

1.1.1 Title

The NICE-SUGAR study is a multi-centre, open label, randomized controlled trial which compares the effects of two regimens targeting either a higher or lower blood glucose concentration in critically ill patients; the targets are a blood glucose concentration between 4.5 - 6.0 mmol/L (lower range), and a blood glucose concentration less than 10.0 mmol/L with insulin infused if blood glucose exceeds 10.0 mmol/L and adjusted when needed to maintain blood glucose between 8.0 – 10.0 mmol/L (higher range).

1.1.2 Patient population

In previous studies of glucose control, the benefit of maintaining blood glucose concentration in the range of 4.4-6.1 mmol/l was limited to ventilated patients who stayed longer in the Intensive Care Unit (ICU) and who were admitted to the study soon after the time of ICU admission.^{1,2} For that reason we will screen all patients admitted to the participating ICUs but exclude those expected to be discharged alive before the end of the day following the day of admission. The attending Intensive Care physician will make this assessment.

We also wish to exclude patients who are expected to stay more than one day in the ICU but who have a very low risk of death. For this reason we will exclude patients who are expected to be eating (or who are tube fed due to pre-existing bulbar or laryngeal dysfunction) by the end of the day after admission and patients whose severity of illness is not great enough to require insertion of an arterial catheter as part of their routine intensive care management. At the other end of the spectrum, we will also exclude patients if they are moribund and at imminent risk of death (brain death or cardiac standstill) on the basis that allocation to either study treatment is unlikely to alter the patient's outcome.

1.1.3 Inclusion criteria

Patients are eligible for **INCLUSION** in the study if BOTH of the following criteria are met:

1. At time of the patient's admission to the ICU the treating ICU specialist expects the patient will require treatment in the ICU that extends beyond the calendar day after the day of admission.
2. The patient has an arterial catheter in situ or placement of an arterial catheter is imminent (within the next hour) as part of routine ICU management.
3. Consent has been obtained or, where delayed consent is allowed, the investigator expects that delayed consent will be obtained.

1.1.4 Exclusion criteria

Patients will be **EXCLUDED** from the study if ONE or MORE of the following criteria are present:

1. Age less than 18 years.
2. Imminent death (cardiac standstill or brain death anticipated in less than 24 hours) and the treating clinicians are not committed to full supportive care. This should be confirmed by a documented treatment-limitation order that exceeds a "not-for-resuscitation" order.

3. Patient admitted to the ICU for treatment of diabetic ketoacidosis or hyperosmolar state.
4. Patient is expected to be eating before the end of the day following admission
5. Patient who has suffered hypoglycaemia without documented full neurological recovery.
6. Patient thought to be at abnormally high risk of suffering hypoglycaemia (e.g. known insulin secreting tumour or history of unexplained or recurrent hypoglycaemia or fulminant hepatic failure)
7. Patient has previously been enrolled in the NICE-SUGAR Study.
8. Patient can not provide prior informed consent, there is documented evidence that the patient has no legal surrogate decision maker and it appears unlikely that the patient will regain consciousness or sufficient ability to provide delayed informed consent. (In some jurisdictions where delayed consent is not permitted – absence of informed consent will be an exclusion criterion)
9. Patient has been in the study ICU or another ICU for longer than 24 hours as part of this ICU admission episode.

There is no upper age limit for inclusion in the study.

1.1.5 Objectives

The primary aim of the study is to compare the effects of the two regimens targeting different blood glucose concentrations on 90-day all-cause mortality in Intensive Care patients who are predicted on admission to the ICU to be treated in the ICU on three consecutive calendar days. The null hypothesis is that there is no difference in the relative risk of death between patients assigned to a target glucose concentration of 4.5 - 6.0 mmol/L and those assigned to target a glucose concentration of less than 10.0 mmol/L with insulin being infused if blood glucose exceeds 10.0 mmol/L, and adjusted when needed to maintain blood glucose of 8.0 – 10.0 mmol/L.

1.1. Unblinding

Access to the interim data/results will be limited to the Data and Safety Monitoring Board (DSMB) members and the statistician(s) in charge of writing the reports. The statistical analysis plan (SAP) will be written by an independent statistician and the principal investigator; both will be blinded to treatment allocations and study results until the final study results are released by the study statistician. Treatment allocations will be stored securely in a separate location for that purpose. Statistician(s) not involved in the writing of DSMB reports will remain blinded and work on dummy treatment until validation of their code has been performed – this will be done in accordance with the Standard Operating Procedures of The George Institute for International Health.

1.2 Definition of the efficacy variables

1.2.1 Definition of primary outcomes

The primary endpoint is all cause mortality 90-days post-randomisation. As loss to follow-up is expected to be minimal, missing values will not be imputed.

In the subset of patients with traumatic brain injury (TBI) defined as CT evidence of traumatic brain injury and a last pre-sedation and pre-randomization Glasgow Coma Scale score of less than 14, mortality is not considered to be the most appropriate outcome. Patients with TBI will be included in the analysis of all cause mortality 90-days post-randomization; in addition, in patients with TBI, the extended Glasgow outcome scale (GOSE) measured at 6 months and two years will be assessed.

The extended Glasgow outcome scale has 8 categories;

- 1 = dead
- 2 = vegetative state
- 3 = lower severe disability
- 4 = upper severe disability
- 5 = lower moderate disability
- 6 = upper moderate disability
- 7 = lower good recovery
- 8 = upper good recovery

For the purpose of analysis the score will be condensed into 4 categories:

- 1 - dead or vegetative state
- 2 - severe disability
- 3 - moderate disability
- 4 - good recovery

Loss to follow-up of patients with traumatic brain injury is expected to be somewhat higher than in the overall population but still less than 10%; missing values will not be imputed.

1.2.2 Definition of secondary outcomes

The secondary outcomes will include:

1. Survival time from randomization to day 90
2. Cause specific mortality within the 90 day follow-up period. Primary cause of death will be categorized into:
 - a. cardiovascular-distributive shock,
 - b. cardiovascular-other,
 - c. respiratory
 - d. neurological-traumatic brain injury,
 - e. neurological-other,
 - f. other
3. Duration of ICU stay - days
4. Duration of hospital stay - days
5. Mechanical ventilation (yes/no) and duration of mechanical ventilation per randomised patient with available data
6. Treatment with renal replacement therapy (yes/no) and duration of renal replacement therapy received per randomised patient with available data.

1.2.3 Definition of tertiary outcomes

1. 28-day all cause mortality
2. Place of death (ICU, elsewhere in hospital, after discharge from hospital)
3. Incidence of new organ failure.
 - a. Respiratory: SOFA* at baseline 0,1 or 2, maximum SOFA >2
 - b. Coagulation: SOFA at baseline 0,1 or 2, maximum SOFA >2
 - c. Liver: SOFA at baseline 0,1 or 2, maximum SOFA >2
 - d. Cardiovascular: SOFA at baseline 0,1 or 2, maximum SOFA >2
 - e. Renal: SOFA at baseline 0,1 or 2, maximum SOFA >2

*SOFA (sequential organ failure assessment score) is a score coded on 0-4 for the 5 domains representing different stages of organ dysfunction (0=normal, 1-2=organ dysfunction 3-4=organ failure). A new organ failure is then identified by a SOFA score of 0-2 at baseline that becomes greater than 2 (maximum >2) further on. A

binary indicator specific to each organ will then be constructed (1 = new failure, 0 = no new failure)

4. Number of patients with positive blood cultures in the ICU from time of randomization to 90 days. This will be identified by a binary indicator with 1 for yes or 0 for no.
5. Number of patients who receive a transfusion of packed red blood cells in ICU and average volume of packed red blood cells received per randomised patient.

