1.4 Analysis principles

1. All analyses will be conducted on an intention-to-treat basis.
2. All tests are two-sided and the nominal level of α will be 5%.
3. All statistical analyses will be unadjusted except where indicated.
4. Subgroup analyses will be carried out irrespective of whether there is a significant effect of treatment on the primary outcome.
5. We will not impute missing values unless specified otherwise. Where the number of missing observations is substantial, we will report the number of observations used in the analysis. Last observations will not be carried forward for continuous outcomes, e.g. the SOFA scores.
6. P-values will not be adjusted for multiplicity. However the outcomes are clearly categorized by degree of importance (primary to tertiary) and a limited number of subgroup analyses are pre-specified.

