2. DESIGN ISSUES

2.1 Data collection Follow-up

The different stages of data collection and follow-up can be summarised in the diagram below:

Form No.	Period of study	Data collection
	Randomization	Patient demographics and inclusion/exclusion criteria
1	Baseline	Source and date of admission to ICU, ICU admission diagnosis, sub-group categorize operative or non-operative admission and presence or absence of 'severe sepsis', 'trauma', traumatic brain injury and patients with Type I or Type II diabetes, Acute Physiology and Chronic Health Evaluation (APACHE) II score, SOFA scores (CVS, respiratory, hepatic, renal, haematologic), use of renal replacement therapy, use of mechanical ventilation, blood glucose concentration (last measurement before randomization), height and weight, prior treatment with insulin and corticosteroids.
2	Hourly, Days 1 - 90	Post-randomization blood glucose concentration whilst in ICU for maximum of 90 days. We will report the overall mean and standard deviation (SD) of daily early morning (first measurement after 08.00) blood glucose and daily time-weighted mean [#] blood glucose concentration measured from randomization to the earlier of ICU discharge or 90 days, the mean and SD early morning (first measurement after 08.00) and time-weighted [#] average blood glucose concentration measured from randomization to the time the patient's blood glucose is no longer managed according to the treatment algorithm (indicating cessation of study treatment). Results will be displayed as a plot of mean over time by treatment arm. They will be truncated at a relevant number of days. e.g. 14 days.
3	Daily, Days 1 - 90	Whilst in ICU: Daily SOFA scores (CVS, respiratory, hepatic, renal, haematologic), treatment with renal replacement therapy or mechanical ventilation, type (enteral versus parenteral) and volume of nutrition administered (total non-protein calories, protein, carbohydrate, lipid will be calculated from type and volume of enteral and parenteral nutrition administered), all iv glucose administered, all positive blood culture results that are clinically significant by predefined criteria. Total amount of insulin administered. Total amount of corticosteroids given (calculated as hydrocortisone equivalent). Number of patients transfused RBCs and volume of red blood cells (RBCs) transfused per randomised patient. Number of patients with treatment limitation order timing of and reason for treatment limitation.

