3.4 Description of analyses

3.4.1 Primary outcome

A standard Chi-square test will be used as the primary test of statistical significance of the effect of treatment allocation on 90-day all cause mortality. Frequencies and percentages per arm, an odds-ratio measuring the treatment effect and its 95% confidence interval (CI) will also be reported. We will also perform an adjusted analysis for sensitivity purposes. It will be based on a multivariate logistic regression analysis adjusted for strata used in minimization, i.e. post-operative versus non-operative patients and region and the following predictors: age, ICU admission source, APACHE II score and mechanical ventilation at baseline. In the event the DSMB considers early stopping of the trial, the results of this analysis will be reported to the management committee and DSMB before a final decision to suspend recruitment is made. A sensitivity analysis will be performed if more than 5% of the 90 day mortality data are missing.

Specific analysis for patients with traumatic brain injury (TBI)

In addition, a specific analysis will be carried out for patients with TBI. In that case the primary outcome will be the GOSE at 2 years. A Wilcoxon rank-sum test adjusted for ties will be used to assess the effect of treatment on the GOSE condensed to four categories listed below:

- 1 - dead or vegetative state
- 2 - severe disability
- 3 - moderate disability
- 4 - good recovery

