3.4.2 Secondary/tertiary outcomes

A standard Chi-square test will be used to assess the effect of treatment on binary or categorical outcomes, i.e. 28-day all cause mortality, cause of death, place of death, incidence of a new organ failure, incidence of positive blood cultures.

Frequencies and percentages per arm, an odds-ratio measuring the treatment effect and its 95% CI will also be reported along with the p-value of the chi-square test.

In addition the number of new organ failures will be tabulated per treatment arm - frequencies and percentages for all values 0-5 new organ failures.

Survival time from randomization to day 90 will be analysed using a Log-rank test. The p-values and a hazard ratio with its 95% CI obtained from a Cox proportional hazards model will also be presented. The proportional hazard assumption across treatment arms will be checked graphically using a log-cumulative hazard plot or the addition of a time-dependent covariate to the model. Probability of survival by treatment group will also be presented as Kaplan Meier curves.

Length of stay in the ICU and the hospital will be censored due to early deaths or a stay in the ICU or hospital of greater than 90 days. They will therefore be considered as times to discharge from the respective unit and analysed with a log-rank test. Summary statistics will include the median and the interquartile range computed separately for each treatment arm. These statistics, when available, will account for censoring – see for instance SAS procedure LIFETEST or comparable tools in other packages. Mechanical ventilation and renal replacement therapy are resource consumption measures and treatments that are not performed on all patients. They will be summarized in two ways: number and percentage of patients per arm who received such a therapy and mean (SD) duration in days per treatment arm. If patients are still being treated with mechanical ventilation or renal replacement therapy at the end of study their data will be censored. The use of packed red blood cell transfusion will be summarized as number and percentage of patients per arm who receive packed red blood cells and mean (SD) volume of packed red blood cells per treatment arm. The effect of treatment allocation will be tested using a two-sample t-test or Wilcoxon rank sum test as appropriate.

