Analyses adjusted for the same predictors as the primary outcome will also be done for the secondary outcomes as subsidiary analyses. They will be based on a linear, logistic or Cox regression as appropriate depending on the type of outcome.

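### The chi-square test for new organ failure ignores the organ's own baseline SOFA level (0, 1 or 2); it is valid but gives up some power if risk rises with that level

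*SAP*

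**What the plan says.** Section 1.2.3 (item 3) sets up five binary outcomes: respiratory, coagulation, liver, cardiovascular and renal. For each, "A new organ failure is then identified by a SOFA score of 0-2 at baseline that becomes greater than 2". The coding is a "binary indicator specific to each organ will then be constructed (1 = new failure, 0 = no new failure".

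Section 3.4.2 gives the test: "A standard Chi-square test will be used to assess the effect of treatment on binary or categorical outcomes". Its list of such outcomes is "28-day all cause mortality, cause of death, place of death, incidence of a new organ failure, incidence of positive blood cultures". An odds ratio with 95% CI accompanies the p-value.

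On adjustment, section 1.4 sets the default: "All statistical analyses will be unadjusted except where indicated". The end of section 3.4.2 makes an exception: "Analyses adjusted for the same predictors as the primary outcome will also be done for the secondary outcomes as subsidiary analyses". New organ failure is tertiary, so the exception does not name it. Even on a wider reading, the predictors in section 3.4.1 are the two minimisation factors plus "age, ICU admission source, APACHE II score and mechanical ventilation at baseline", with no organ SOFA score.

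The score itself is held. The baseline form in section 2.1 lists "SOFA scores (CVS, respiratory, hepatic, renal, haematologic), use of renal replacement therapy", and section 3.2 (item 16) tabulates all five components by arm.

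**The concern.** The outcome and the unused covariate are the same scale in the same organ. A patient who starts at 2 needs one more point to count as a new failure; a patient who starts at 0 needs three. The SAP's own note calls 0 normal and 1-2 dysfunction, so the at-risk group mixes normal and already impaired organs. The starting level is therefore likely to predict the event, and APACHE II, a global score, is not a substitute for it.

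If risk does rise with starting level, part of the outcome variance lies between levels. An unstratified test leaves that part in its standard error, and a stratified test removes it. At stake is some power in five tertiary comparisons, recoverable from data the trial already holds.

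**Working it through.** **The plan's own figure.** The SAP states no rate, power or precision for organ failure. Its only power statement (section 2.4) concerns mortality: 6100 patients, 90% power, 30% against 26.2%. The two-proportion formula gives 5878 patients in total without continuity correction and 5982 with it, and 91.0% power at 3050 per arm. The statement is sound and does not bear on this point.

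**Inputs.**
- From the SAP: 6100 patients; two-sided 5% level (section 1.4).
- Assumed: 1:1 allocation, so 3050 per arm; 80% at risk in a given organ, so 0.80 × 3050 = 2440 per arm; baseline levels 0/1/2 in shares w = 50/25/25%; conditional odds ratio 0.80 at every level; control risks by level as tabulated below. Patients at baseline SOFA 3-4 are left out, because they cannot have the event.

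**Formulas.** With control risk p at a level, the other arm has q = 0.8p / (1 − p + 0.8p). Let P and Q be the w-weighted averages of p and q, and D = P − Q.
- Unstratified variance: V = M(1 − M), with M = (P + Q)/2.
- Stratified variance: W = Σ w·m(1 − m), with m = (p + q)/2 at each level.
- Power = Φ(D / √(2V/n) − 1.96) for the chi-square, with W in place of V for a Mantel-Haenszel test.

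**Worked case, control risks 6/14/30%.** The q are 4.86%, 11.52% and 25.53%. P = 0.1400, Q = 0.1169, D = 0.0231. V = 0.1120 and W = 0.1037. The standard errors of D are √(2 × 0.1120/2440) = 0.00958 and √(2 × 0.1037/2440) = 0.00922. D divided by these is 2.41 and 2.50, so power is 67.3% and 70.6%.

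| Control risk at 0/1/2 | V/W | Power, chi-square | Power, stratified | Crude OR | SE of log OR, crude | SE of log OR, adjusted |
|---|---|---|---|---|---|---|
| 10/12/15% | 1.00 | 66.7% | 66.9% | 0.801 | 0.0931 | 0.0932 |
| 8/12/20% | 1.02 | 66.1% | 67.0% | 0.804 | 0.0921 | 0.0931 |
| 6/14/30% | 1.08 | 67.3% | 70.6% | 0.813 | 0.0859 | 0.0893 |
| 4/14/40% | 1.18 | 63.4% | 70.7% | 0.828 | 0.0819 | 0.0892 |

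V/W is the sample-size equivalent: 1.08 corresponds to about 8% more patients.

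**Where the gain appears.** It is in the power of the test and in the precision of a risk difference or standardised estimate. The conditional log odds ratio has a larger standard error than the crude one in all four rows (1%, 4% and 9% larger in the last three). Power rises because the conditional odds ratio lies further from 1 than the crude one.

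**Validity and sensitivity.** In 40,000 simulated trials (2000 per arm, shares 40/30/30%, risks 5/15/35%), type I error was 5.0% for the chi-square and 5.2% for the stratified test. At odds ratio 0.80, power was 63.4% and 68.2%. By formula at 2000 per arm, a near-flat gradient of 10/12/15% (shares 50/25/25%) moves power from 58.2% to 58.3%. A very steep one of 2/15/60% (shares 34/33/33%) moves it from 54.5% to 70.5%.

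**The case against.** The strongest reply is that nothing here is wrong. The chi-square is valid, needs no model, agrees with the raw percentages and matches both the primary test and the SAP's general rule on adjustment. The outcome is tertiary, and the gain depends wholly on rates the SAP does not give; with a near-flat gradient it vanishes. All of this stands, and it limits the point to an optional improvement.

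Four stronger readings are tempting, and the SAP does not support them.
- A reader might infer bias, because baseline SOFA is not a minimisation factor. But chance imbalance is already in the chi-square's variance, which is why its type I error holds at 5%. With 25% of patients at level 2, the standard error of the difference between arms in that share is √(2 × 0.25 × 0.75/2440), about 1.2 percentage points.
- A reader might infer that adjustment would narrow the interval for the odds ratio that section 3.4.2 reports. For a conditional odds ratio it does not.
- A reader might infer that the unadjusted test has no merit. Its simplicity and its consistency with the other binary outcomes are real advantages.
- A reader might take these comparisons as the main evidence on morbidity. Section 1.2.2 ranks ventilation, renal replacement therapy and length of stay above them, and section 1.4 says the outcomes are ordered by importance.

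What the reply does not answer is that a probable predictor, already collected, is left out of the analysis.

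**Conclusion.** The point holds as a minor matter of efficiency. The SAP tests each organ's new failure without using that organ's starting level, and no adjusted analysis in the plan uses it either. If risk rises with starting level, power is lost: about 0 to 1 percentage point with a weak gradient, and about 3 to 7 points with the steeper ones tabulated at 2440 per arm. These figures assume the at-risk number, the level shares, the risks by level and a common conditional odds ratio of 0.80. The SAP fixes none of them, and a more extreme gradient would widen the range. No contradiction, bias or inflation of the type I error has been shown.

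**What to change.** Add to section 3.4.2: for each organ, among patients with baseline SOFA 0-2 in that organ, test new failure with a Mantel-Haenszel test (or a logistic model) stratified by that organ's baseline level, with 0, 1 and 2 as categories. Report a risk difference or odds ratio standardised over baseline level with its 95% CI. Keep the raw counts, percentages and unadjusted chi-square alongside. Naming the at-risk group also settles something the 1/0 coding leaves open, namely whether patients already at SOFA 3-4 are counted as 0 or left out.

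The cost is one sentence and five simple analyses, with no new data. If a conditional odds ratio is reported instead of a standardised one, it will differ slightly from the crude value and its interval on the log scale will not be narrower; the text should say so. Specifying this in advance also avoids a choice after the fact should the arms differ by chance in starting level.
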